#### 4.9.2 Operation Precautions of Obstetric Cesarean Section

In cesarean section, the absorption of amniotic fluid should be sufficient, so that the residual of intrauterine amniotic fluid can be minimized. When cut the umbilical cord, cord blood should be guaranteed not to enter the uterine cavity. Any action that makes fetal bleeding should be avoided.

Prepare two sets of suction equipment, one for amniotic fluid and other.

#### 4.9.3 Anesthesia Cell Salvage Operation (See Appendix 3)

### 4.10 About Early Termination of Trial

If the blood collection machine manufacturer issues an important safety notice, then we will temporarily stop the trial. If the ethics committee, the national clinical trial management agency, or the funders need to suspend the trial due to the consideration for subjects' maximum benefit or the trial itself, then the principal investigator will receive a written notice, and stop the trial. Usually the concerns will involve safety, efficacy of the trial, violations of relevant provisions and protocol, etc.

### 4.11 About the Ending of Trial

The ending time of Phase I in this trial is defined as the date that the last subject discharges from hospital. The ending time of Phase II in this trial is defined as when the last subject exceeded the childbearing age and has been followed for 10 years. At the end of trial, we will notify the Ethics Committee. The final study report will be completed within six months after the end of trial.

## 5 Cell Salvage Equipment

- 5.1 Blood Collection Machine (National certified washing cell salvage machine)
- 5.2 Leucocyte Filter

## 6 Laboratory(Biochemical Test)

### 6.1 Centers/Local Laboratory

The test is basically conducted in the local laboratory. Only part of the blood samples will be sent to the Second Affiliated Hospital of Wenzhou Medical University (Central Laboratory) for testing (eg, fetal components from maternal and cell salvage). It can be raised individually if anything else needs to be submitted to the Central Laboratory.

### 6.2 Sample Collection/Marking/Registration

Sample:

- a. In operating room, take the peripheral blood of maternal before anesthesia and after transfusion, 8ml respectively;
- b. self-salvaged blood, 8ml.

Using EDTA or other anticoagulant whole blood, samples from other hospitals can be placed in a refrigerator at 4 °C, prepare within 48h.

Symboling and registering the samples with the unique study number.

### 6.3 Sample Reception/Management/Responsibility

Before sample processing, all samples need to be checked in by laboratory personnel. Once any error is found, it will be returned to the sample collector or research team.

## 6.4 Sample Analysis Process

6.4.1. Set 8ml blood sample with NH4Cl lysis solution for 30min (Due to the large amount required and several bottles of commercial hemolysin may be required, it is preferred to formulate NH3CL by self.). The sample is centrifuged at 2000 rpm for 5 minutes at room temperature and the supernatant is discarded;

6.4.2. Use perfix-nc kit, punch and fix. (The usage reference of perfix-nc kit is specified in kit instructions);

6.4.3. Antibody, CD45PECY7 / CD71-PE / HBF-FITC / 7-AAD (30ul / antibody) is added and incubated for 20 minutes;

6.4.4. Use up-flow cytometer to circle non-cellular impurity groups, calculate the value of fluorescence;

6.4.5. Use upstream cytometer to sort and select cells that expressing CD45- / CD71 + / HBF + / 7-AAD + at a rate of 30,000 cells per second or above (Due to large background mass of the sample cells, the time required to sort each sample at an effective sorting rate of 25-30 thousands cells per second is between 1 and 1.5 hours, so we need to ensure that cells are not lost and are complete, and try to improve the effective sorting speed);

6.4.6. Receive and accept the sorted fetal with nucleated red blood cells in the 100 ulPCR centrifuge tube;

6.4.7. Fetal has nucleated red blood cell count.

## 6.5 Sample Preservation Process(if needed)

Keep autologous blood samples until 3 years after the end of the study

## 6.6 Results Report and Registration Time

All sample results need to be truthfully recorded in the original record sheet and ECRF. If needed, the test results can be printed to the original record sheet.

## **7 Safety of Trial (Adverse Events)**

### **7.1 Definitions**

#### **7.1.1 Adverse Events (AE)**

An adverse event (AE) is any untoward medical occurrence in a patient or clinical investigation subject administered a pharmaceutical product and which does not necessarily have a causal relationship with this treatment. An adverse event can therefore be any unfavourable and unintended sign, an abnormal laboratory finding, symptom, or disease temporally associated with the use of a medicinal (investigational) product.

#### **7.1.2 Severe Adverse Events (SAE)**

In trials, if any untoward medical occurrence, it is defined as severe adverse event.

- death of maternal or fetus (note: death is a termination indicator, not an event)
- Is life-threatening
- after caesarean section, causes prolongation of existing hospitalization for more than 7 days by adverse event
- results in persistent or significant disability/incapacity
- fetus has congenital abnormalities or defects
- investigators think it is a severe medical event

### **7.2 Investigator's Assessment of Adverse Events**

#### **7.2.1 Seriousness of Assessment**

The principal investigators at each center are responsible for participants' medical treatment. If the principal investigator is unable to observe the abnormality, the authorized physician in this test team is responsible for assessing the severity of the adverse events as described in 7.2.4.

### **7.2.2 Causal Analysis**

Investigators must assess the causal relationship between all adverse events and the trial.

### **7.2.3 Urgency of Report**

Investigators must assess the prognosis of all severe adverse events. If the cause of this serious adverse event is unpredictable related to the trial, it must be reported immediately.

### **7.2.4 Severity of the Adverse Events**

According to the criteria described below, investigators need to assess the severity of the adverse events. The severity grades of the event can not be confused with the word 'serious' in a serious adverse event(SAE). 'Severity' is defined based on the patient / event outcome criteria.

- ◆ General: observed discomfort but does not affect subject's daily life
- ◆ Moderate: the level of discomfort is sufficient to affect or reduce the level of activity of a normal person
- ◆ Serious: completely unable to carry out daily activities, and seriously affected the normal life.

## **7.3 Record and Report of Adverse Event**

If the adverse event is not rated as a serious adverse event, then the adverse event needs to be recorded in the appropriate place or adverse event testing registration form for participant's record. The research team also needs to track the progress of the participants.

## **7.4 Record and Report of Severe Adverse Event**

All serious adverse events found in the trial or reported by the participants themselves, whether related to the trial or not, need to be recorded in the participants' case report forms and adverse event registration forms. All serious adverse events need to be followed until a new solution appears or the event is stable. Investigators need to provide follow-up information. All serious adverse events that are related to the withdrawal of the participants or happen at the end of the trial, need to be tracked until a satisfactory solution has been found.

After cesarean section, due to adverse events resulting in the longest hospital stay than 7 days, we need to be considered as prolonged hospitalization, and recorded in the

serious adverse events record form or adverse events record form.

According to local regulations, in each center, it is the major investigators' responsibility to report serious adverse events to the principal investigators and their local authorities. All serious adverse events need to be reported to the principal investigator within 24 hours of occurrence. Within 24 hours, PI needs to give feedback to quality control managers and sponsors of the Practical Clinical Trial Unit (PCTU) about all relevant or unanticipated serious adverse events. Within 15 days, or within the time as requested by the sponsor or PCTU, PI is required to report a serious adverse event to the General Ethical Committee.

#### **7.4.1 Expected Adverse Events**

Although no serious adverse events are expected, it is still possible.

Risks of trial operation include:

- Maternal exposed to baby's blood
- Amniotic embolism
- Severe hypotension
- Transfusion reaction

For participants, the frequency of these risks is unlikely to increase substantially. Based on the criteria for a serious adverse event, if these risks meet the criteria for a serious adverse event, they are also reported as serious and unexpected adverse events.

### **7.5 Annual Safety Report**

Principal investigators need to send an annual safety report to the Ethics Committee (MREC). The principal investigator needs to report annually to the Ethics Committee about all relevant and unexpected serious adverse events in tabular form with time order. Meanwhile, this form is reported to Data monitoring & Safety monitoring committee and Trial Steering Committee every 6-12 months.

## **8 Statistical Analysis**

### **8.1 Estimation of Sample Size**

#### **8.1.1 Sample Size Calculation**

In this study, we use data from control group (donor blood transfusion) to estimate the sample size, and then use 1: 1 ratio to calculate the sample size of IOCS sample.

The calculation is shown below:

A pilot study has commenced at the The 2nd Affiliated Hospital of Wenzhou Medical University, Zhejiang Province, China, involving women having Caesarean sections and the need for red cell transfusion. We collected a sample of 50 from the study and use the following formula to estimate the blood loss after the caesarean section:

Blood loss =  $BV * (Hct_{first\ day\ post\ operation} - Hct_{xth\ day\ post\ operation}) + Vt$   
 where BV is the blood volume, Vt is the volume of red cell (unit: ml), and Hct has a unit with decimal places.

### 1. Sample Statistics for Donor Blood

#### Transfusion

N	effective	48
	missing	0
mean		444
median		274
SD		709
minimum		0
maximum		4347
percentiles	25	0
	50	274
	75	700

### 2. Sample Size Estimation Based On Population Mean

$$n = \left(\frac{t_{\alpha/2} s}{\delta}\right)^2$$

If  $t_{0.05}=1.96$ ,  $S=709$ ,  $\delta=200$ , the estimated minimum sample size is 50.

3. Thus, according to ratio 1:1, the sample size of IOCS group is also 50.

4. Taking into account the unpredictable factors in the experiment that cause the loss of sample size, we recommend to use 1.2 times the minimum sample size as the sample minimum sample size. Therefore, according to ratio 1:1 between treatment group and control group, the total sample size would be 120 (where 60 for treatment group, and 60 for control group).

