## 4.9 Relevant Operating Plan

### 4.9.1 Assessment Method for Intraoperative and Postoperative haemorrhage in Obstetrics

- Assessment Method for Intraoperative blood loss in Cesarean Section
  - ❖ Weighing Method: blood loss (ml)  $\approx$  (weight of gauze with blood – weight of dry gauze) /1.05
  - ❖ Measuring Cup Method: used to measure amount of blood in a curved plate; blood loss ml=Volume of measuring cup (blood clots crush as much as possible).
  - Intraoperative blood loss = Recycling machine blood volume (recovery machine capacity - flushing, washing capacity) + Placental bleeding (using measuring cup to measure the amount of blood flow into the curved plate by

- squeezing the placenta) + blood volume of cleaning the vagina (bleeding with weighing method, blood clots with measuring cup method) + blood volume of gauze (bleeding with weighing method, blood clots with measuring cup method)
- Postoperative blood loss = blood volume of postpartum sterile mattress + blood volume of gauze (bleeding with weighing method, blood clots with measuring cup method) + volume of shed blood (using measuring cup)

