## 8.2 Outcomes

### 8.2.1 Primary Outcomes

- Blood loss post operation

Hb and Hct in first and fifth day after surgery.

The direct measurement of is the accurate volume of blood loss in major haemorrhage is difficult. Alternatives such as haemoglobin (Hb) or hematocrit (Hct)

are more frequently used and blood loss can be calculated using these parametres. Since Hct or Hb will be recorded as per standard practice during and postoperative in the hospital.

In this proposed trial, we are planning that Hb and Hct in the first and fifth day after the surgery as the primary outcome to reflect the blood loss.

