## 8.3 Statistical Methods

### 8.3.1 General Principle

Using SAS 9.13 for statistical analysis. All statistical tests should be two-sided. If p-value is less or equal to 0.05, then it is considered to be statistically significant.

Variables data are described by mean±standard deviation, median, maximum and minimum. Use paired t-test to compare intra-group variations with respect to baseline and use ANOVA or Wilcoxon rank-sum test to compare variations between groups.

Attributes data are described as frequency (percentage). Between group comparison of percentages is tested by Fisher's exact test

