### 8.3.2 Significance Level

Use superiority test to compare the primary objective between groups. The significance level  $\alpha= 0.05$  (two-sided).

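### The stated minimum of 50 per arm comes from a formula for the precision of one arm's mean, not from the planned two-arm superiority test

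*Combined protocol and SAP*

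**What the plan says.** Section 8.1.1 opens by stating that "we use data from control group (donor blood transfusion) to estimate the sample size". The pilot table (item 1) describes donor-transfusion women only: 48 effective values, mean 444, median 274, SD 709, 25th percentile 0, maximum 4347. Item 2 sets n equal to the square of (critical value × s / δ), with 1.96, 709 and 200, and concludes that "the estimated minimum sample size is 50". Item 3 adds that "the sample size of IOCS group is also 50", by the 1:1 ratio. Item 4 multiplies by 1.2 for losses, so that "the total sample size would be 120 (where 60 for treatment group, and 60 for control group").

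The comparison to be made is set out later. Section 8.3.2 says: "Use superiority test to compare the primary objective between groups", at a two-sided 0.05 level. Section 8.3.3 specifies a log-rank test and a Cox hazard ratio for the amount of postoperative blood loss, while Section 8.3.1 says to "use ANOVA or Wilcoxon rank-sum test to compare variations between groups".

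Section 8 states no power. It does not say whether 200 ml is a precision or a difference to detect.

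**The concern.** The formula in item 2 answers how many women are needed to pin down the mean loss in a single group. A superiority test asks whether two means, or two distributions, differ. That needs a target difference, a variance for each arm and a stated power, and none of these enters the calculation. Setting the second arm equal to the first does not turn the one into the other, because the variance of a difference is the sum of two variances.

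The result is nevertheless labelled a minimum and is the only justification given for 120. A reader can reasonably take 60 per arm as adequate for the superiority test, when the plan never shows what that test could detect. If the true detectable difference is close to the whole control mean, a non-significant result would be compatible with a large benefit, and the protocol gives no warning of it.

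**Working it through.** **Inputs from the documents.** s = 709, control mean 444, minimum and 25th percentile 0, maximum 4347, 48 values (8.1.1, item 1); δ = 200 and critical value 1.96 (item 2); 50 per arm, or 60 after inflation (items 2 to 4); two-sided α = 0.05 (8.3.1, 8.3.2). **Assumptions of this check:** 80% power as a benchmark, and an IOCS-arm SD, which the plan does not give.

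**1. The plan's own figure.** (1.96 × 709 / 200)² = 6.948² = 48.3. With a t quantile on 47 df (2.012) it is 50.9. The stated 50 lies between the two, 50 × 1.2 = 60, and 2 × 60 = 120. There is no arithmetic slip.

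**2. What that formula secures.** The half-width for one arm's mean at n = 50 is 1.96 × 709 / √50 = 196.5 ml (201.5 ml by t). The ±200 ml therefore belongs to one arm.

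**3. Precision of the between-arm difference, SD 709 in both arms.** SE = 709 × √(2/n), which is 141.8 at n = 50 and 129.4 at n = 60. Half-width = t(0.975, 2n − 2) × SE:
- n = 50: 1.984 × 141.8 = 281.4 ml
- n = 60: 1.980 × 129.4 = 256.3 ml

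Holding ±200 ml on the difference takes 2 × 48.3 = 96.6 per arm by z, or 98 by t.

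**4. Difference detectable with 80% power (noncentral t).** 401.2 ml at n = 50 and 365.6 ml at n = 60. As a share of the pilot control mean, 401/444 = 90% and 366/444 = 82%.

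**5. Power, only if 200 ml is the difference to detect.** 200/141.8 = 1.41 and 200/129.4 = 1.55 standard errors, giving power of 28.7% and 33.5%. By the normal approximation, 80% power for 200 ml would take 2 × (1.96 + 0.84)² × (709/200)² ≈ 198 per arm.

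**6. Sensitivity to the SD.** The alternatives below are assumptions, not in the plan.
- *IOCS SD falling with its mean:* after a 200 ml reduction, 709 × 244/444 = 390.
- *Pilot maximum removed:* dropping 4347 from 48 values with mean 444 and SD 709 leaves mean 361 and SD 419. That one value's squared deviation is (4347 − 444)² / (47 × 709²) = 64% of the sum of squares.
- *Both together:* 419 × 161/361 = 187 in the IOCS arm.

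Each cell is for 50 / 60 per arm, with Welch df where SDs differ. Detectable differences hold the SDs fixed at the values shown.

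| SD control vs IOCS | Half-width (ml) | 80% detectable (ml) | Power at 200 ml |
|---|---|---|---|
| 709 vs 709 | 281 / 256 | 401 / 366 | 29% / 34% |
| 709 vs 390 | 228 / 207 | 325 / 296 | 41% / 47% |
| 419 vs 419 | 166 / 152 | 237 / 216 | 66% / 74% |
| 419 vs 187 | 130 / 118 | 184 / 168 | 86% / 92% |

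If in the second row the IOCS SD keeps scaling with the mean instead of staying at 390, the detectable difference is 300 / 277 ml.

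**7. The test in Section 8.3.3.** Log-rank power needs a hazard ratio, an event count and a censoring rule. The plan gives none, so no figure follows from it.

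**The case against.** The strongest reply is that the millilitre figures describe an analysis the plan does not name as primary. Section 8.3.3 specifies log-rank/Cox. If blood loss is the time axis and every woman contributes an observed value, events equal women, and the 80%-detectable hazard ratio is exp(2 × 2.80 / √N), about 1.75 with 100 women and 1.67 with 120. This is a fair conditional calculation, but the no-censoring condition is not in the plan. Nor does it rescue item 2, whose formula matches the log-rank test no better than a comparison of means.

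Second, SD 709 in both arms is pessimistic at the detectable differences quoted. Falls of 401 or 366 ml from 444 leave an IOCS mean of 43 or 78 ml, and an SD of 709 around such a mean is implausible for losses that in the pilot go no lower than 0. This stands as a caution: the 90% and 82% shares depend partly on the common SD, and the data are skewed enough for normal-theory figures to be approximate. That is why the range is shown. However, 709 is the only SD the plan uses, and it offers no basis for a smaller one.

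Third, Section 8.1.1 is open about being based on a mean and on control data, and it claims no power. True, but it still calls the result a minimum and builds the trial size on it.

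Fourth, the endpoint could be called clear enough, since Sections 2.1.1 and 8.3.3 both name blood loss. But Section 8.2.1 plans "Hb and Hct in the first and fifth day after the surgery as the primary outcome", and Section 4.9.1 defines a measured quantity ("Postoperative blood loss = blood volume of postpartum sterile mattress" plus further components). The millilitre figures apply only if the haematocrit-calculated loss is what is analysed.

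**Conclusion.** The concern holds. The sizing formula and the planned test do not match, and this is certain from the text: 50 reproduces as a one-mean precision size and not as a two-arm size.

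How much it matters is conditional. For a comparison of means at the plan's own SD in both arms, the half-width of the difference is 281 / 256 ml at 50 / 60 per arm and the 80%-detectable difference is 401 / 366 ml. Under the most favourable SDs considered, the detectable difference falls to 184 / 168 ml. If 200 ml is meant as a target difference, power lies anywhere from about 29% to 92% across the SD assumptions and the two sample sizes. The plan gives no basis for choosing within that range. It is therefore not shown that the trial is underpowered; it is shown that the plan does not support its stated minimum. None of these figures carries over to the log-rank/Cox rule. The statement needs correcting, because it is the only rationale given for the size of a superiority trial.

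**What to change.** Keep 120 women and change the text, in this order.

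1. Settle the primary endpoint and its test. Reconcile Section 8.2.1 (Hb and Hct on two days, or blood loss calculated from them) with the measured loss in Section 4.9.1, and Section 8.3.1 (ANOVA/Wilcoxon) with Section 8.3.3 (log-rank/Cox).
2. In Section 8.1.1, describe 50 as a one-arm precision size, not as the minimum for the superiority comparison. Say whether 200 ml is a precision or a target difference.
3. State what 60 per arm (50 evaluable) delivers for the retained test.
   - *Comparison of mean blood loss:* lead with the half-width of 256 (281) ml and the 80%-detectable difference of 366 (401) ml at SD 709. If 200 ml is a target difference, add the power of 34% (29%), with the SD sensitivity range beside it and a note that the SDs are held fixed.
   - *Log-rank/Cox:* state the hazard ratio, event count and censoring rule on which its power rests.

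Two small additions would help: say how a non-significant result will be read, and reconcile the pilot count (50 in the text, 48 in the table).

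The cost is protocol wording only, with no change in the number of women. The stated properties will look less favourable, and they cannot be written in until step 1 is done.

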## 8.2 Outcomes

### 8.2.1 Primary Outcomes

- Blood loss post operation

Hb and Hct in first and fifth day after surgery.

The direct measurement of is the accurate volume of blood loss in major haemorrhage is difficult. Alternatives such as haemoglobin (Hb) or hematocrit (Hct)

are more frequently used and blood loss can be calculated using these parametres. Since Hct or Hb will be recorded as per standard practice during and postoperative in the hospital.

In this proposed trial, we are planning that Hb and Hct in the first and fifth day after the surgery as the primary outcome to reflect the blood loss.

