### 8.2.2 Secondary Outcomes

- PT/APTT, Hct and Hb in first and fifth day after surgery
- the number of units of donor blood transfused
- mean fall in serum haemoglobin level
- maternal morbidity resulting from postoperative anaemia
- time to first mobilisation,
- duration of hospital stay
- immediate multidimensional fatigue inventory.
- Total cost in hospital

Second Stage: Follow-up when pregnancy again:

Neonatal hemolytic disease (Appendix 2)

Determine blood type, antibody, and IgG titer)

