### 8.3.3 Hypothesis Test

Primary objective: The amount of blood lose post operation:

$$H_0: HR = \frac{\lambda_T}{\lambda_C} < 1, \quad H_1: HR = \frac{\lambda_T}{\lambda_C} \geq 1$$

$\alpha = 0.05$  (two-sided).

By Log-Rank test, if p-value is less or equal to 0.05, and the median amount of blood lose in treatment group is less than in control group, then the superiority of the treatment group relative to the control group holds.

Based on the Cox Proportional hazards model, hazard ratios and the 95% confidence interval (CI), if the lower bound of the CI is greater than 1, then the efficacy of the treatment group is better than that of the control group.

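### Section 8.2.1 calls four Hb/Hct values primary while 8.3.3 tests only blood loss, and no hierarchy stops a laboratory result being reported as primary if the blood-loss test fails

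*Combined protocol and SAP*

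**What the plan says.** The documents assign the primary role in two different ways.

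- **Laboratory values as primary.** Section 8.2.1 carries a blood-loss bullet, but then says "we are planning that Hb and Hct in the first and fifth day after the surgery as the primary outcome". Taken literally, that is Hb on day 1, Hb on day 5, Hct on day 1 and Hct on day 5.
- **The same values as secondary.** Section 8.2.2 lists "PT/APTT, Hct and Hb in first and fifth day after surgery", and section 2.1.2 has the same entry among the secondary objectives.
- **Blood loss as primary.** Section 2.1.1 gives one primary objective, blood loss over five postoperative days. Section 8.3.2 says "Use superiority test to compare the primary objective between groups", at two-sided 0.05. Section 8.3.3 identifies it as "Primary objective: The amount of blood lose post operation" and sets the only superiority criterion in the plan on that quantity.
- **The general rule.** Section 8.3.1 says "All statistical tests should be two-sided" and "If p-value is less or equal to 0.05, then it is considered to be statistically significant". It provides ANOVA or the Wilcoxon rank-sum test for between-group comparison of continuous variables, which would include Hb and Hct.

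Sections 8.1 to 8.3 contain no order of testing, no requirement that all four values succeed, and no adjustment for several tests.

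**The concern.** A trial report may describe as primary whatever the plan calls primary. Here that label covers both a blood-loss quantity with a formal hypothesis and four laboratory values without one. If the blood-loss comparison were not significant but Hb on day 5 had p = 0.04, the authors could cite 8.2.1 and 8.3.1 and present a prespecified, significant primary outcome. Nothing in 8.3.2 or 8.3.3 forbids this. The 0.05 stated in 8.3.2 would then no longer describe the chance of a false primary claim. A reader of the report could not tell from the plan which result was meant to decide the trial.

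**Working it through.** **1. The plan's own error rate.** Section 8.3.2 sets two-sided alpha at 0.05. One test that rejects when |Z| > 1.96 has a false-positive probability of 0.05 under no effect. With blood loss as the only deciding test, the stated figure is reproduced: 5%.

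**2. Independent tests, each at 0.05.** The chance of at least one p ≤ 0.05 among k tests is 1 − 0.95^k.

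- Four laboratory values: 1 − 0.95^4 = 0.185.
- Four values plus the blood-loss test: 1 − 0.95^5 = 0.226.

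**3. Correlated tests.** Hb and Hct on the same day are closely related, so independence overstates the figure. The documents give no correlations. The following are assumptions: Hb–Hct on the same day 0.80, 0.90, 0.95 or 0.98, and day 1–day 5 0.3, 0.5, 0.7 or 0.8. The four test statistics were drawn from a multivariate normal distribution (1,000,000 draws per setting), counting the share with any |Z| > 1.96. The blood-loss statistic was built from the standardised Hct day 1 minus day 5 difference with weight 1, 0.7, 0.5 or 0, the remainder being independent.

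| Hb–Hct | Day 1–day 5 | Four values | Four values plus blood loss |
|---|---|---|---|
| 0.80 | 0.3 | 14.6% | 16.8–18.9% |
| 0.90 | 0.5 | 12.6% | 15.4–17.0% |
| 0.95 | 0.5 | 11.6% | 14.5–16.0% |
| 0.95 | 0.8 | 10.0% | 13.8–14.5% |
| 0.98 | 0.8 | 9.2% | 13.1–13.7% |

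Over all 16 settings the range is 9.2–14.6% for the four values and 13.1–18.9% with blood loss added.

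**4. Plausibility check.** If Hb duplicated Hct completely, two tests (Hct on day 1 and on day 5) would remain. Their joint error in the same simulation is 7.8–9.5%, so high correlation between Hb and Hct does not bring the rate back to 5%.

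**5. Direction.** These are two-sided figures, comparable with the stated 0.05. Section 8.3.3 also requires the lower median in the treatment group, so the one-directional benchmark is 0.05 / 2 = 2.5%. Counting only favourable results, the four values give 4.6–7.4%.

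**6. Is blood loss itself uniquely defined?** Two derivations stand in the documents.

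- Section 8.1.1 multiplies blood volume by the fall in Hct from day 1 to an unspecified later day and adds the red-cell volume. It uses Hct only; Hb does not enter. It is introduced for the pilot data behind the sample size.
- Section 4.9.1 obtains postoperative loss by weighing gauze and by measuring cup, with no time window stated. The procedure table in 4.8 schedules postoperative bleeding for collection.

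Section 8.2.1 does not say which of these yields the endpoint.

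**The case against.** The strongest reply is that there is only one primary endpoint and that Hb and Hct merely feed it. Section 8.2.1 says "blood loss can be calculated using these parametres" and introduces the values as "Hb and Hct in the first and fifth day after the surgery as the primary outcome to reflect the blood loss". Section 8.1.1 has a formula of that kind, the sample size is set on blood loss, and the only superiority rule (8.3.3) concerns blood loss. The p ≤ 0.05 convention in 8.3.1 says when a test is called significant, not which test decides the trial.

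Much of this stands. Under the formal rule the nominal error is 5%, and no section says that a significant Hb or Hct value establishes superiority. A reader might infer that the primary claim already carries an error of 11–13%, or that each of the four values is a declared route to success. The documents do not support either reading. Any inflation depends on a reporting choice that the plan leaves open, and the size depends on correlations that the plan does not give. A figure of 11–13% also corresponds only to four tests with very high Hb–Hct correlation, not to four tests plus blood loss.

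The inputs reading does not remove the problem, however. Hb has no place in the only formula, yet it is named primary on both days. Section 8.2.1 does not adopt that formula, and 4.9.1 measures blood loss in another way. Listing Hb and Hct again as secondary outcomes treats them as results in their own right.

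**Conclusion.** The plan contradicts itself on what the primary outcome is and has no rule to settle it. That much rests on the text alone. The effect on the error rate is conditional:

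- 5% if only the 8.3.3 blood-loss test counts;
- about 9–15% if any one of the four Hb/Hct values could count (18.5% if independent);
- about 13–19% if the blood-loss test could count as well (22.6% if independent).

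The ranges rest on the assumed correlations above and on normally distributed test statistics. The exact percentage matters less than the open choice behind it. The matter should be settled before the data are analysed.

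**What to change.** - In 8.2.1, name one confirmatory endpoint, blood loss over five postoperative days, matching 2.1.1, and test it once at two-sided 0.05. Section 8.3.3 gives both a log-rank criterion and a Cox interval criterion, so state which one decides.
- State the single derivation of that endpoint. Reconcile the Hct formula in 8.1.1 with the weighing and measuring-cup method in 4.9.1, and fix the start and end of the period. If the formula is used, keep Hct in 8.2.1 only as an input to it.
- List Hb and Hct on days 1 and 5 in 8.2.2 only (and 2.1.2 accordingly), reported as supportive estimates with 95% confidence intervals.

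If the sponsor wants the laboratory values to remain primary, a multiplicity procedure must be specified in advance. For example, Bonferroni at 0.05 / 4 = 0.0125 for the four values, or 0.05 / 5 = 0.01 with blood loss included, holds the error at or below 5%, at a price in power.

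The recommended change is one of wording and needs no new data. Its downside is that the sponsor gives up the option of claiming primary success on an Hb or Hct value.
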